10.2.6.9 Treatment Dose Modifications and Guidelines for Hypertension

Increases in blood pressure (BP) have been observed in subjects receiving trametinib. Should initiation of anti-hypertensive therapy be required, single agent therapy (commonly including the calcium channel blockers amlodipine or nifedipine) should be started and the blood pressure should be monitored at least twice weekly until BP is within the 95th percentile for age, height, and gender ([Appendix V](#)).

If subject is already on an anti-hypertensive medication at study enrollment, then their anti-hypertensive therapy should be adjusted (by either adjusting the dose of their current anti-hypertensive medication or by adding another anti-hypertensive agent) according to the algorithm in [Section 10.1.6.11](#).

[figure not shown]
10.2.6.10 Screening Blood Pressure

- Screening blood pressure (BP) is defined as the blood pressure obtained at the examination used for study enrollment. BP should be obtained as follows: Obtain blood pressures from the same extremity with the subject in the same position at rest with an appropriately sized cuff. Avoid using the lower extremity if possible.

10.2.6.11 Management of Hypertension

- The upper limit of normal (ULN) is defined as a BP equal to the 95th percentile for age, height, and gender. ([Appendix V](#))
- The NCI CTCAE v5.0 will be utilized to determine the grade of hypertension for reporting purposes.
- Elevated BP measurements should be repeated on the same day to confirm the elevation. Subjects with an elevated BP should have BP measurements performed at least twice weekly until BP is \leq ULN.
- The algorithm below will be used to manage trametinib related hypertension.

- Hypertension should be managed with appropriate anti-hypertensive agent(s) as clinically indicated. It is strongly recommended that nephrology or cardiology be consulted in the evaluation and management of hypertension.

Elevations in BP are based on systolic or diastolic pressures.

†Elevated blood pressure measurements should be repeated on the same day to confirm the elevation. Subjects with elevated BP at any time should have BP measurements performed at least twice weekly until BP is within the ULN.

§ULN is a BP equal to the 95th percentile for age, height, and gender-appropriate normal values ([Appendix V](#)).

*If BP > 25 mm Hg above ULN for age (verified) or Grade 4 hypertension at any time, hold drug. Study drug should also be held for BP ≥ 25 mm Hg above the ULN for 14 days or ≥ 35 mm Hg above baseline for > 14 days. Antihypertensive agents can be used to control hypertension as clinically indicated after study drug is held.

^ Antihypertensive therapy should be prescribed as clinically indicated, including use of multiple anti-hypertensive agents.

#Screening BP as defined in [Section 10.1.6.10](#)

Arm 1 of algorithm:

- If blood pressure (BP) ≤ 95thile for age, height, and gender: continue trametinib at the same dose.

Arm 2 of algorithm:

- If BP ≤ 10 mm Hg above the ULN: continue trametinib at the same dose and recheck the BP within 72 hours.
 - If the BP is ≤ ULN on recheck, continue trametinib at the same dose.

- If the BP remains above the ULN on recheck, then start/adjust antihypertensive therapy and follow Arm 3 of the algorithm from the point that anti-hypertensive therapy is started/adjusted.

Arm 3 of algorithm:

- If BP is 11 to 25 mm Hg above the ULN on ≥ 2 of 3 measurements or > 35 mmHg above baseline on ≥ 2 of 3 measurements, start/adjust anti- hypertensive therapy and continue trametinib at the same dose. Monitor BP at least twice weekly.
 - If the BP returns to \leq ULN within 14 days, continue trametinib at the same dose and continue anti-hypertensive therapy.
 - If the BP remains elevated ≥ 25 mmHg above the ULN or > 35 mmHg above baseline for more than 14 days after the institution/adjustment of anti-hypertensive therapy, hold trametinib, monitor BP at least every 3 days, and follow Arm 4 of the algorithm from the point that trametinib is held. The anti-hypertensive therapy should be continued until the BP is less than the ULN.
- If the BP returns to \leq ULN within 14 days, restart trametinib at reduced dose (See [Appendix II](#)).
- If the BP remains $>$ ULN for more than 14 days, subject must be removed from protocol therapy.
 - If the BP increases to > 25 mm Hg above the ULN despite anti-hypertensive therapy, hold trametinib, but continue the anti-hypertensive agent(s). Monitor the BP as clinically indicated and follow Arm 4 of the algorithm from the point that trametinib is held.

Arm 4 of algorithm:

- If BP is > 25 mm Hg above the ULN hold trametinib, monitor BP, and administer/adjust antihypertensive therapy as clinically indicated.
 - If the BP returns to \leq ULN within 14 days, trametinib may be restarted at a reduced dose.
 - If the BP is $>$ ULN for > 14 days, the subject must be removed from protocol therapy

Arm 5 of algorithm:

- If the subject develops Grade 4 hypertension, discontinue trametinib, monitor BP and administer anti-hypertensive therapy as clinically indicated. The subject is Off Protocol Therapy.

10.2.6.12 *Treatment Dose Modifications and Guidelines for Paronychia*

Management of Paronychia:

Systemic antibiotics can be used for initial treatment of paronychia. For recurrent paronychia, or paronychia involving other additional digits flurandrenolide (e.g. Cordran) tape or a topical steroid cream such as triamcinolone can be used in the morning and mupirocin and ketoconazole topical ointments in the evening. If no improvement is seen, a dermatology or surgery consultation is recommended. For infected lesions, bacterial and fungal culturing followed by the appropriate culture-driven systemic or topical antibiotics is indicated. Rarely, surgical removal of the nail may be necessary as clinically indicated.

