17	95th	125	126	127	129	130	131	132	82	83	83	84	85	85	86

Instructions for using this BP Chart:

1. Measure the subject's blood pressure using an appropriate size cuff.
2. Select appropriate chart for female or male subject.
3. Using the "age" row and "height" column determine if the BP is within the ULN.
4. See [Section 10.1.6.9](#) for definition of dose modifying hypertension. See [Section 10.1.6.11](#) for management and grading of hypertension.

Note: For subjects ≥ 18 yrs, ULN BP is 140/90 mmHg.

This table was taken from "The Fourth Report on the Diagnosis, Evaluation, and Treatment of High Blood Pressure in Children and Adolescents" PEDIATRICS Vol. 114 No. 2 August 2004, pp. 555-576.

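### In the written hypertension algorithm, a BP at or below the ULN but more than 35 mm Hg above baseline meets both Arm 1 and Arm 3, and no precedence is stated

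*Protocol*

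**What the plan says.** - **ULN.** Protocol 10.2.6.11: "The upper limit of normal (ULN) is defined as a BP equal to the 95th percentile for age, height, and gender". Appendix V adds that for subjects aged 18 and over "ULN BP is 140/90 mmHg".
- **Arm 1.** For BP at or below that percentile: "for age, height, and gender: continue trametinib at the same dose". A rise from baseline is not excepted.
- **Arm 3, entry.** BP 11 to 25 mm Hg above the ULN or, as an alternative, "> 35 mmHg above baseline on ≥ 2 of 3 measurements". The alternative carries no ULN condition. The action is to start or adjust antihypertensives and keep the trametinib dose.
- **Arm 3, after 14 days.** If BP comes back to the ULN or below within 14 days, the dose is kept. The hold rule has two limbs: at least 25 mm Hg above the ULN, or "> 35 mmHg above baseline for more than 14 days after the institution/adjustment of anti-hypertensive therapy, hold trametinib".
- **Starred footnote.** Its hold also applies at "≥ 35 mm Hg above baseline for > 14 days", again with no ULN condition.
- **Restart.** After a hold, Arm 3 restarts at a reduced dose once BP is at or below the ULN within 14 days. Arm 4 permits that restart.
- **Re-escalation.** Section 10.2.3 bars it after a reduction for toxicity unless 10.2.6 provides otherwise. The rash, LVEF and pneumonitis text does so; the hypertension text does not.
- **Baseline.** The algorithm does not define it. Section 10.2.6.10 defines screening BP as the "blood pressure obtained at the examination used for study enrollment", and a note to the algorithm refers to that section.

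**The concern.** Arms 1 and 2 classify a subject by distance from the ULN. Arm 3 adds a second yardstick, change from baseline, without saying how the two combine. A subject whose BP has risen a good deal from a low starting point, but is still within the protocol's own limit, receives two instructions.

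At first the arms differ only on antihypertensives, because both keep the trametinib dose. After 14 days they differ on trametinib itself: Arm 1 continues it, while Arm 3 and the footnote hold it.

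With 25 sites and 39 evaluable subjects, two sites could treat identical subjects differently. One subject might be untreated at full dose, the other on an antihypertensive and at a lower dose that cannot be raised again. If this happened before the end of cycle 6, it would alter exposure at the primary endpoint. The event could also be classified differently, since it does not meet the specific definition of dose-modifying hypertension in 10.2.1.1.

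**Working it through.** The plan gives no figure to reproduce. The check is whether the written conditions can hold together, and for whom.

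**Inputs.** Arm 1: BP ≤ ULN. Arm 3, baseline limb: BP > baseline + 35. Footnote: BP ≥ baseline + 35. ULN values come from Appendix V (median height for minors; 140/90 from age 18).

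**Condition for overlap.** Both arms apply when baseline + 35 < BP ≤ ULN. In whole mm Hg this requires baseline ≤ ULN − 36.

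| Group | ULN | Highest systolic baseline | Highest diastolic baseline |
|---|---|---|---|
| 18 and over | 140/90 | 140 − 36 = 104 | 90 − 36 = 54 |
| Boy, 17 | 136/87 | 100 | 51 |
| Girl, 17 | 129/84 | 93 | 48 |
| Boy, 12 | 123/81 | 87 | 45 |
| Boy, 5 | 112/72 | 76 | 36 |
| Boy, 1 | 103/56 | 67 | 20 |

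Either the systolic or the diastolic value can bring a subject into Arm 3. The required baselines become remote in young children.

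**Worked case.** Adult, screening systolic 100, on-study 138 on at least two of three readings, diastolic within 90 throughout.

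1. 138 ≤ 140, so Arm 1 applies: same dose.
2. 138 − 100 = 38 > 35, so Arm 3 applies: start or adjust antihypertensives.
3. If systolic is still 138 more than 14 days after therapy starts, the hold rule is met, since 138 > 100 + 35 = 135. Arm 1 still says to continue.
4. After a hold, BP is already at or below the level required for restart. If trametinib is restarted, it is at a reduced dose, and 10.2.3 then bars re-escalation.
5. Arm 3 continues antihypertensives until BP is below the ULN, which was already so before they began.

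**Footnote against Arm 3.** With the same baseline and an on-study value of 135, the rise is exactly 35. The footnote's limit is met and Arm 3's is not.

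**Section 10.2.1.1.** Dose-modifying hypertension is Grade 4, or more than 25 mm Hg above the 95th percentile. For an adult the second means above 140 + 25 = 165 systolic, so 138 does not meet it. The general statement in the same section, that any dose modification for toxicity counts as dose-modifying, would capture the subject once the dose is changed.

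**How narrow the window is.** For an adult with systolic baseline 104, only an on-study value of 140 qualifies; for 100, values 136 to 140; for 95, values 131 to 140.

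**The case against.** The algorithm is also drawn as a figure that is not reproduced in the text reviewed, and an order of branches may be shown there. So the absence of precedence can be asserted only of the prose. The arms can also be read as escalating steps, with the baseline limb a deliberate extra trigger for a large rise. The section concerns trametinib-related hypertension and leaves antihypertensives to clinical indication. These points show that a workable reading may exist. They do not show that the text states it: the written hold and dose steps are directive, and the baseline limb is an explicit alternative to the ULN limb.

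Several stronger readings are not supported:

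- **Two opposite day-14 outcomes within Arm 3.** The same-dose rule speaks of BP returning to the ULN or below, which poorly fits a subject who was never above it. The firm conflict is between Arm 1 and Arm 3.
- **Immediate restart.** No text says this. The restart criterion is already met, but Arm 4 only permits a restart.
- **A sizeable share of adults affected.** If adult screening systolic BP is assumed to have mean 110 to 115 and SD 10, the share at 104 or below is 27.4% to 13.6% (z = −0.6 to −1.1). The distribution is an assumption, not in the protocol. The result is the share whose baseline makes the overlap possible, not the share in whom it occurs.
- **Arm 2 as an equal problem.** Arm 2 sends a BP still above the ULN at the 72-hour recheck to Arm 3, so that overlap matters less.
- **An effect on the toxicity stopping rule.** Section 9.2 counts Grade 4 hypertension, which this overlap does not touch.

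**Conclusion.** The point holds for the written text. A BP at or below the ULN but more than 35 mm Hg above baseline meets Arm 1 and Arm 3, with no written precedence. The footnote repeats the hold with a slightly different limit. A subject whose BP never exceeded the protocol's ULN could have trametinib held and then resumed at a reduced dose that may not be raised again.

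The reach is limited. The overlap needs a baseline at least 36 mm Hg below the ULN (adult systolic 104 or less, or diastolic 54 or less) and a rise on at least two of three readings. A hold under Arm 3 also needs persistence beyond 14 days on therapy. It is reachable mainly in adolescents and adults and probably affects few subjects; the protocol does not allow the number, or any effect on cycle 6 exposure, to be estimated.

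This rests on taking baseline to be the screening BP and on the prose alone, without the figure. It is a contradiction between instructions; which of them is clinically right is not judged here.

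**What to change.** Reconcile Arms 1, 2 and 3, the starred footnote, the algorithm figure and 10.2.1.1 so that each combination of BP and baseline leads to one action. The text should state:

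- whether the baseline limb applies when BP is at or below the ULN, and how it relates to Arm 2;
- which day-14 outcome governs when BP is at or below the ULN but still above the baseline limit;
- one form of the 35 mm Hg limit, used in both Arm 3 and the footnote;
- that baseline means the screening BP of 10.2.6.10, if that is intended;
- whether a hold or reduction reached through the baseline limb counts as dose-modifying hypertension under 10.2.1.1.

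The choice of clinical rule is the sponsor's. The cost is a wording amendment and a matching correction to the figure where needed, with no added procedures or visits and no change to the sample size.

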APPENDIX V: BLOOD PRESSURE

Blood Pressure Levels for Children by Age and Height Percentile

Blood pressure (BP) levels for Boys:

Age (years)	BP Percentile	Systolic Blood Pressure, mm Hg							Diastolic Blood Pressure, mm Hg						
		Percentile of Height							Percentile of Height						
		5th	10th	25th	50th	75th	90th	95th	5th	10th	25th	50th	75th	90th	95th
1	95th	98	99	101	103	104	106	106	54	54	55	56	57	58	58
2	95th	101	102	104	106	108	109	110	59	59	60	61	62	63	63
3	95th	104	105	107	109	110	112	113	63	63	64	65	66	67	67
4	95th	106	107	109	111	112	114	115	66	67	68	69	70	71	71
5	95th	108	109	110	112	114	115	116	69	70	71	72	73	74	74
6	95th	109	110	112	114	115	117	117	72	72	73	74	75	76	76
7	95th	110	111	113	115	117	118	119	74	74	75	76	77	78	78
8	95th	111	112	114	116	118	119	120	75	76	77	78	79	79	80
9	95th	113	114	116	118	119	121	121	76	77	78	79	80	81	81
10	95th	115	116	117	119	121	122	123	77	78	79	80	81	81	82
11	95th	117	118	119	121	123	124	125	78	79	80	81	82	82	83
12	95th	119	120	122	123	125	127	127	78	79	80	81	82	82	83
13	95th	121	122	124	126	128	129	130	79	79	80	81	82	83	83
14	95th	124	125	127	128	130	132	132	80	80	81	82	83	84	84
15	95th	126	127	129	131	133	134	135	81	81	82	83	84	85	85
16	95th	129	130	132	134	135	137	137	82	83	83	84	85	86	87
17	95th	131	132	134	136	138	139	140	84	85	86	87	87	88	89

Blood pressure (BP) levels for Girls:

Age (years)	BP Percentile	Systolic Blood Pressure, mm Hg							Diastolic Blood Pressure, mm Hg						
		Percentile of Height							Percentile of Height						
		5th	10th	25th	50th	75th	90th	95 th	5th	10th	25th	50th	75th	90th	95th
1	95th	100	101	102	104	105	106	107	56	57	57	58	59	59	60
2	95th	102	103	104	105	107	108	109	61	62	62	63	64	65	65
3	95th	104	104	105	107	108	109	110	65	66	66	67	68	68	69
4	95th	105	106	107	108	110	111	112	68	68	69	70	71	71	72
5	95th	107	107	108	110	111	112	113	70	71	71	72	73	73	74
6	95th	108	109	110	111	113	114	115	72	72	73	74	74	75	76
7	95th	110	111	112	113	115	116	116	73	74	74	75	76	76	77
8	95th	112	112	114	115	116	118	118	75	75	75	76	77	78	78
9	95th	114	114	115	117	118	119	120	76	76	76	77	78	79	79
10	95th	116	116	117	119	120	121	122	77	77	77	78	79	80	80
11	95th	118	118	119	121	122	123	124	78	78	78	79	80	81	81
12	95th	119	120	121	123	124	125	126	79	79	79	80	81	82	82
13	95th	121	122	123	124	126	127	128	80	80	80	81	82	83	83
14	95th	123	123	125	126	127	129	129	81	81	81	82	83	84	84
15	95th	124	125	126	127	129	130	131	82	82	82	83	84	85	85
16	95th	125	126	127	128	130	131	132	82	82	83	84	85	85	86

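### In the hypertension algorithm, Arm 3's 14-day hold is nearly empty on its ULN limb, leaving a gap whose width depends on baseline, and Grade 4 hypertension carries conflicting instructions

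*Protocol*

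**What the plan says.** Protocol 10.2.6.11 sorts subjects by BP relative to ULN, defined as the 95th percentile for age, height and gender.

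- **Arm 2:** up to 10 mm Hg above ULN. If BP is still above ULN at recheck, antihypertensive treatment is started or adjusted and the subject follows Arm 3.
- **Arm 3 entry:** 11 to 25 mm Hg above ULN, or more than 35 above baseline, on at least 2 of 3 measurements. Antihypertensive treatment is started or adjusted, trametinib continues at the same dose, and BP is checked at least twice weekly.
- **Arm 3, back to ULN or below within 14 days:** continue.
- **Arm 3, 14-day hold:** BP at least 25 mm Hg above ULN, or more than 35 above baseline, "for more than 14 days after the institution/adjustment of anti-hypertensive therapy, hold trametinib".
- **Arm 3, last bullet:** "If the BP increases to > 25 mm Hg above the ULN despite anti-hypertensive therapy, hold trametinib".
- **Arm 4:** BP more than "25 mm Hg above the ULN hold trametinib, monitor BP, and administer/adjust antihypertensive therapy as clinically indicated". A reduced restart is possible if BP returns to ULN within 14 days; otherwise the subject is removed.
- **Footnote to the algorithm:** "If BP > 25 mm Hg above ULN for age (verified) or Grade 4 hypertension at any time, hold drug". It then repeats the 14-day hold as at least 25 above ULN for 14 days, or at least 35 above baseline for more than 14 days.
- **Arm 5:** "If the subject develops Grade 4 hypertension, discontinue trametinib, monitor BP and administer anti-hypertensive therapy as clinically indicated". The subject is then off protocol therapy.

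Elsewhere, 10.2.1.1 lists Grade 4 hypertension as a dose-modifying toxicity, and 10.2.3 manages such toxicities by a hold and possible resumption at the next lower dose. For Grade 4 events in general, 10.10 allows either permanent discontinuation or interruption followed by a reduced dose.

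**The concern.** A threshold that acts after 14 days should catch subjects whom the immediate threshold does not. Here the two ULN thresholds almost coincide, so the delayed rule does little in the band that Arm 3 was written for. A subject whose BP improves but does not reach ULN may then have no stated trametinib decision at day 14.

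Grade 4 hypertension is a separate matter: a hold, an end to protocol therapy and a reduced restart can each be read from the text.

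Both bear on patient safety and on who remains on drug, in a trial planned for 25 sites. Section 1.2.2 lists hypertension among the most common adverse events of trametinib monotherapy in adults.

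**Working it through.** The plan states no figure for this point, so there is nothing to reproduce. The check enumerates the written rules in whole mm Hg.

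**Inputs from 10.2.6.11**

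- Immediate hold: more than 25 above ULN (footnote, Arm 3 last bullet, Arm 4).
- 14-day hold in Arm 3: at least 25 above ULN, or more than 35 above baseline.
- Continue: at or below ULN.

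**Notation.** Let x be the mm Hg above ULN sustained for more than 14 days after antihypertensive treatment was started or adjusted. Let g be ULN minus baseline BP. The rise above baseline is then x + g. The protocol gives no baseline BP, so g is an assumption and is varied from 0 to 35.

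**Step 1: the ULN limb.** Values with x ≥ 25 that are not already held at once (x > 25) reduce to x = 25. This limb adds one value.

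**Step 2: the unassigned range.** No branch applies when x ≥ 1, x ≤ 24 and x + g ≤ 35. The upper end is therefore min(24, 35 − g).

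| g (mm Hg) | 35 − g | Range above ULN with no branch |
|---|---|---|
| 0 | 35 | 1–24 |
| 10 | 25 | 1–24 |
| 11 | 24 | 1–24 |
| 15 | 20 | 1–20 |
| 20 | 15 | 1–15 |
| 25 | 10 | 1–10 |
| 30 | 5 | 1–5 |
| 35 | 0 | none |

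The values 1 to 10 count because Arm 2 subjects still above ULN at recheck are sent into Arm 3.

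**Step 3: footnote against Arm 3.** On the ULN limb the footnote says 14 days and Arm 3 says more than 14. On the baseline limb the footnote says at least 35 and Arm 3 says more than 35. With the footnote's operator the upper end becomes min(24, 34 − g), for example 14 instead of 15 at g = 20. The difference is 1 mm Hg, but the same hold is stated in two ways.

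**Step 4: Grade 4 hypertension, side by side**

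| Place | Instruction |
|---|---|
| 10.2.6.11 footnote | hold |
| 10.2.6.11 Arm 5 | discontinue; off protocol therapy |
| 10.2.1.1 with 10.2.3 | hold; may resume at a reduced dose |
| 10.10 | discontinue permanently, or interrupt and reduce |

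**Step 5: the ULN source.** Appendix V, "Blood Pressure Levels for Children by Age and Height Percentile", runs from age 1 to 17, with a note giving one value for age 18 and over. Inclusion criterion 2 in 5.1 admits subjects from 2 months.

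**The case against.** **A printed line may fill the gap.** Under Arm 3 there is also a line removing a subject whose BP remains above ULN for more than 14 days. Read as a direct Arm 3 branch, it covers the whole gap. But it is paired with a line about restarting at a reduced dose, which presupposes a hold, and Arm 4 repeats the same pair after its own hold. As a direct branch it would also remove a subject slightly above ULN while the bullet before it only holds one at 25 or more. It is best read as following a hold. Its indentation cannot be relied on in the extracted text, and the algorithm figure was not available, so its position needs to be made clear.

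**The gap is not unsupervised.** This stands. The opening instruction continues to apply, twice-weekly checks run until BP is at or below ULN, multiple agents are permitted, and nephrology or cardiology consultation is strongly recommended. Section 10.2.1.1 treats certain Grade 3 toxicities, and persistent Grade 2 toxicities that need interruption, as dose-modifying. Section 10.4.1 lets the physician remove a subject. A reader might infer that raised BP continues with no oversight; the text does not support that.

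**Grade 4 may be reconcilable.** The footnote's hold could be the first action and Arm 5 the disposition, and 10.2.1.1 points to the special-interest guidance in 10.2.6. That argument orders the general sections behind 10.2.6.11. It does not settle the footnote against Arm 5, which stand in the same section. The footnote also joins Grade 4 to the category above 25 mm Hg, for which Arm 4 allows a restart.

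**The infant rule exists.** ULN is defined by percentile, so only the printed lookup is incomplete. This stands, and the point is secondary.

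**Conclusion.** The concern holds in a limited form. On its ULN limb, Arm 3's 14-day hold adds only the value of exactly 25 mm Hg. BP that stays above ULN by less than 25, and not more than 35 above baseline, for more than 14 days on antihypertensive treatment has no branch beyond the opening instruction to continue and monitor. This rests on reading the removal line as post-hold and on the text without the figure.

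A reader might infer that every value from 1 to 24 mm Hg above ULN lacks an outcome. That is true only when baseline lies within 11 mm Hg of ULN. With a lower baseline, the limb tied to baseline assigns a hold to the upper part of the range, and at a difference of 35 mm Hg nothing is left. The ranges count mm Hg values, not patients, and the protocol offers no basis for saying how many subjects would fall in them.

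The different wording of the 14-day hold and the conflicting Grade 4 instructions are confirmed from the text. A reader might also infer a shift in the cycle 6 response result. The route is plausible, since disposition determines who is still on drug, but the documents give nothing from which its size could be calculated. The severe-toxicity pause rule in 9.2 counts a treatment-associated Grade 4 event in the first two courses whatever its disposition, so that count is unaffected.

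**What to change.** Reconcile the footnote, Arms 3, 4 and 5 of 10.2.6.11, the algorithm figure, 10.2.1.1 with 10.2.3, and 10.10, so that:

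1. every BP range above ULN after 14 days of antihypertensive treatment has one stated instruction, including BP that has not returned to ULN but meets no hold criterion;
2. the line removing subjects who remain above ULN for more than 14 days shows which branch it belongs to;
3. the 14-day hold has a single wording, with the same durations and operators wherever it appears;
4. Grade 4 hypertension has one instruction in all of these places.

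Which cut-off and which disposition apply is a clinical decision for the sponsor; this review does not choose between them.

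As a secondary edit, state in Appendix V the source of ULN for subjects under 1 year.

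The cost is a text amendment and a check of the figure. Twice-weekly BP measurement for elevated readings is already required, so no added visits or measurements are implied.
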